9.2 SETTING

9.2.1 Definitions

Study Period: the entire period of time that includes the baseline period, the cohort entry date (index date), and follow-up period for the study population. The study period will be from **01 April 2015** (180 days prior to Spiolto approval date of 28 September 2015 in Japan) to **31 March 2019** (end of available data).

Patient Selection Period: the period of time for which patients are eligible to enter the cohort. The earliest date of the patient selection period is **28 September 2015**, (the Spiolto approval date in Japan). The latest date of the patient selection period is 31 December 2018, corresponding to 90 days before the end of available data (31 March 2019), ensuring that all patients have at least 60 days after the cohort entry date to identify a second prescription for index therapy and at least 30 days to be capable of the 30-day overlap to determine the triple therapy initiation outcome.

Cohort Entry Date: Date of entry to the initial cohort of Tio/Olo vs. Tio users (*first prescription*).

Baseline Period: the 180-day period that ends 1 day prior to the cohort entry date used to assess covariate information. The earliest start of the baseline period would be 01 April 2015, corresponding to 180 days prior to the approval date of Spiolto.

[figure not shown]
Follow-Up Period: the period starting at the second prescription for Tio/Olo or Tio within 60 days of the cohort entry date (first prescription) and ending at the earliest occurrence of the outcome (use of triple therapy), or the first occurrence of inpatient death, disenrollment, or end of the study period (31-Mar-2019). A sensitivity analysis will employ an as-treated censoring approach to further censor upon discontinuation of index therapy or initiation of the other index treatment arm. Patients may have different lengths of follow-up (i.e. variable follow-up).

Since health care is nationalized in Japan, the notion of enrollment is not applicable. Therefore, a proxy enrolment criterion defined as start of enrolment = date of first inpatient/outpatient encounter; end of enrolment = date of last inpatient/outpatient encounter will be used. “Enrolment” herein will refer to this proxy enrolment measure. For entry into the study population, patients will be required to have had at least 180 days of enrollment prior to the cohort entry date.

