9.3.2 Outcomes

9.3.2.1 Primary outcomes

Triple Therapy Use

[figure not shown]
The primary outcome of interest is incident rate of triple therapy initiation (first event per patient) defined as any LAMA/LABA/ICS fixed dose combination or any concurrent use for 30 consecutive days of the following:

- any LAMA/LABA fixed dose combination + any ICS single formulation
- any LAMA single formulation + any LABA/ICS fixed dose combination
- any LAMA single formulation + any LABA single formulation + any ICS single formulation

MDV data has limited information on treatment duration with the days of prescription recorded as 1 day for most patients. Therefore, a days supply of 30 days will be assumed. Although we will require at least 30 days of overlap, the first date of triple therapy overlap will serve as the outcome event date, as corresponds to the initiation of triple therapy. Looking into the future to satisfy the requirement of overlap for at least 30 days has the potential to inflict immortal person-time, but is necessary to differentiate concurrent use when subsequent medication is added (see [Figure 3](#) - example Patient A) from an early sequential prescription fill when subsequent medication is switched to (see [Figure 3](#) - example Patient B).

Figure 3

Illustration of outcome

Censoring

Patients will be censored if they had an occurrence of any of the following: outcome (initiation of triple therapy), death, or end of data. The analysis will use an intention-to-treat censoring approach, which does not account for treatment change. A sensitivity analysis will employ an as-treated censoring approach to further censor upon discontinuation of index therapy or initiation of the other index treatment arm. Thus, events will be assigned to exposure groups according to that patient's original index medication, even if that patient discontinued or crossed over.

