9.6 DATA MANAGEMENT

Dataset

The Medical Data Vision dataset is comprised of administrative records of longitudinal inpatient, outpatient and drug data from multiple hospitals that have been standardized and de-identified prior to use for the analysis. The statistical analysis will be conducted using the

COPD Maintenance Therapy Drug Duration

Given limited information on treatment duration in the MDV data, a days supply of 14 days will be assumed for “Spiolto Respimat 28puffs.” Otherwise, 30 days will be assumed for all LAMA, LABA, and ICS maintenance therapies, including “Spiriva Inhalation Capsules 18microg”, “Spiriva 2.5microg Respimat 60puffs 150microg”, “Spiriva 1.25microg Respimat 60puffs 75microg”, and “Spiolto Respimat 60puffs”. A grace period of 14 days between assumed end of days supply and subsequent prescription will be used as an allowable gap.

Handling of Missing Data

Missing data that occurs in covariates or descriptive variables will be classified as its own level (i.e. missing data indicator). In addition, a feasibility assessment before beginning the

analyses will be done, and variables with >75 % missing values will be excluded from all analyses, other than baseline characteristics. If a variable is left with only one level other than missing, the variable will be excluded completely from all analyses.

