To assess the primary outcome of triple therapy among those who are not on triple therapy fixed dose combination or filling all the three medications at the same time, an algorithm will be employed to assess the concurrent use (previously described). This algorithm will require us to look into the future to determine the start of the triple therapy and may introduce bias. However, it requires an overlap of only 30 days, and it is unlikely to significantly affect the results.

The primary analysis is being conducted as an Intention to Treat (ITT) approach in which patients are analyzed according to first exposure. However, it is likely that some patients may discontinue their COPD medication or switch over to another cohort. The misclassification of exposure may bias the results. A sensitivity analysis using On Treatment approach will be conducted, which will take into account discontinuation and switching of cohort from one medication to the other.

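### Overlap-defined triple therapy needs 30 later days to be confirmed, but at-risk time is not shortened at the end of follow-up, so absolute rates may be understated by between almost nothing and about 8%

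*Combined protocol and SAP*

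**What the plan says.** Section 9.3.2.1 defines the primary event as "any LAMA/LABA/ICS fixed dose combination or any concurrent use for 30 consecutive days of the following", and then lists three multi-inhaler routes. A triple fixed combination therefore counts at once; the other routes need an overlap. On dating, the section says: "Although we will require at least 30 days of overlap, the first date of triple therapy overlap will serve as the outcome event date". Because recorded durations are mostly one day, supply is imputed: "Therefore, a days supply of 30 days will be assumed". Section 9.6 adds: "A grace period of 14 days between assumed end of days supply and subsequent prescription will be used as an allowable gap".

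Section 9.2.1 ends follow-up at the earliest of the outcome, inpatient death, disenrollment and 31-Mar-2019. Enrolment is a proxy: "end of enrolment = date of last inpatient/outpatient encounter will be used". Two other places differ. The censoring list in Section 9.3.2.1 omits disenrollment, and Section 9.9 treats patients as observable over the whole data range.

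Section 9.7.1.2 divides first events by all person-years in follow-up, with no deduction. Section 9.2.1 does allow for the overlap at entry, by closing recruitment early enough to leave "at least 30 days to be capable of the 30-day overlap to determine the triple therapy initiation outcome". Section 9.12 says of the look-ahead in the outcome algorithm that "it requires an overlap of only 30 days, and it is unlikely to significantly affect the results".

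**The concern.** An event dated on day t by the overlap route can be declared only with information about the 30 days that follow. If observation stops before day t + 30, the event may be missed, yet the person-time around day t stays in the denominator. The same logic that led the sponsor to close entry early applies to every patient's last 30 days, and there the protocol makes no allowance.

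Two things are at stake. Rates, risks and rate differences come out too low. The event definition also changes within a patient's follow-up: near its end, triple fixed combinations still count while some overlap events do not, so the mix of events depends on how and when observation stops. None of the five sensitivity analyses in Section 9.7.3 would show this.

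**Working it through.** **1. Entry allowance.** 31-Dec-2018 + 60 days = 1-Mar-2019, the latest start of follow-up given under Figure 1. Adding 30 days gives 31-Mar-2019, the end of data. The 30 days are thus secured after the latest possible first day at risk. They are not secured for later risk time, nor for patients who die or have their last encounter earlier.

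**2. Which overlaps need a later record.** Imputed supply is 30 days. Components prescribed on the same day are credited with exactly 30 days of overlap. If one component was filled d days before the add-on, it has 30 − d days left, so the overlap falls short unless a refill is seen. The 14-day grace period bridges a gap only when a subsequent prescription exists. Mid-supply add-ons therefore need a later refill under any reading. Same-day starts need one only if supply may not run past the end of follow-up, which the protocol does not say.

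**3. Share of person-time in the last 30 days.** The protocol gives no mean follow-up, so it is assumed.
- Administrative censoring only: uniform entry over 28-Sep-2015 to 31-Dec-2018 (1,190 days) puts mean entry 595 + 90 = 685 days before data end. Less an assumed 30 days to the second fill, this leaves 655 days, or about 1.8 years. Share: 30/655 = 4.6%.
- Mean follow-up of 1 year because of censoring at last encounter: 30/365 = 8.2%.

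With a roughly constant hazard, these are ceilings on the understatement of overlap-event rates.

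**4. Simulation.** 40,000 patients per arm, with hazards from the 6% and 10% one-year figures in Section 9.5. All events are taken as overlap events, and in the as-written column none is confirmable in the last 30 days. Rates per 1,000 person-years are given as Tio, Tio/Olo:

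| Follow-up ends at | Mean days | Every event seen | As written | Last 30 days cut |
|---|---|---|---|---|
| Data end only | 577, 603 | 103.0, 61.4 | 99.1, 58.7 | 103.6, 61.4 |
| Data end or last encounter (0.5 per year) | 365, 375 | 105.8, 61.1 | 98.6, 56.8 | 106.3, 61.4 |

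The falls are 1 − 99.1/103.0 = 3.8% and 1 − 58.7/61.4 = 4.4% in the first row. In the second they are 1 − 98.6/105.8 = 6.8% and 1 − 56.8/61.1 = 7.0%. The second-row rate difference goes from 44.7 to 41.8, and the cut gives 44.9. If half the tail events are confirmable, the second-row rates are 102.6 and 59.2, a fall of about 3%.

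**5. Hazard ratio (Tio/Olo v Tio).** With equal follow-up in the second scenario it is 0.578 with every event seen, 0.577 as written and 0.577 with the cut. If Tio/Olo patients enter later (mean 247 v 365 days), it is 0.574, 0.541 and 0.572.

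**6. Power.** Section 9.5 states 141 events for a hazard ratio of 1.73 at 90% power. Schoenfeld's formula, 4(1.960 + 1.282)²/(ln 1.73)², gives 140, and 141 events give power 0.902. Losing the full 30/365 leaves 141 × (1 − 0.082) = 129 events and power 0.877; losing half leaves 135 events and power 0.890.

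**The case against.** The best counter-argument is the imputation. Overlap is built from assumed supply, not observed days, so one visit at which all components are prescribed could meet the rule even at the last encounter. No section says that supply stops at the end of follow-up, and Figure 3, which illustrates the algorithm, was not available in the text reviewed. This stands: the lower end of the effect is near nil. It does not remove the point, because the entry rule reasons as if 30 days of data are needed and mid-supply add-ons need a refill in any case.

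Second, the last-encounter tail is not settled. If Sections 9.3.2.1 and 9.9 govern, the uncut tail lies only before death or 31-Mar-2019, and the size is closer to 4–5%. This also stands.

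Third, the main comparison is a Cox hazard ratio. A reader might infer that it is biased towards Tio/Olo. The documents do not support that: the shift in step 5 needs unequal follow-up, which was assumed. Calendar year of index is in both propensity scores (Section 9.2.2), which tends to balance administrative follow-up after matching. An unequal escalation route remains possible. For instance, Section 9.3.1 lists the 28-puff Tio/Olo pack at both 14 and 30 days' supply, while Section 9.6 has 14. At 14 days, even a same-day ICS start needs a refill to reach 30.

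Finally, a reader might take Section 9.12 as dismissing this very problem. It addresses looking ahead to date the start of triple therapy, not person-time at the end of follow-up.

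**Conclusion.** The point holds as a correctable bias in absolute measures. Overlap-event rates and rate differences are understated by an amount running from near nil, through about 4–5% with administrative censoring only, to about 8% at a mean follow-up of 1 year. Crude risks lose a similar share of events: in the second scenario, 6,271 of 6,735 are counted, a loss of 6.9%. The upper figures assume a roughly constant hazard, end of observation unrelated to escalation, no tail event confirmable and no triple fixed combinations; each fixed-combination event reduces the effect.

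A reader might go further and say that tail events cannot be confirmed at all, or quote 16% (30 days against a mean of half a year). The first ignores the imputed supply, and nothing in the documents supports so short a follow-up. The primary hazard ratio and the power are little affected unless follow-up length or escalation route differs by arm. The change is still worth making before analysis because it is cheap and removes the bias in the rates.

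**What to change.** - **At-risk time.** For the primary outcome, end it 30 days before the last observable date, for events and person-time alike. That date is the earliest of inpatient death, proxy disenrollment (if it is a censoring event) and 31-Mar-2019. Use later data only to confirm overlap.
- **Rules to settle.** Reconcile Sections 9.2.1, 9.3.2.1 and 9.9 on censoring at last encounter. State whether imputed supply beyond the last observable date can complete an overlap. Reconcile the supply assigned to the 28-puff pack in Sections 9.3.1 and 9.6.
- **Sensitivity analysis.** Report the uncut analysis beside the main one, and give follow-up length and triple-therapy route by arm.

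The cost is a short change to the follow-up definition, with three downsides. Fixed-combination events in the last 30 days are lost, and the protocol gives no count of these. Patients whose last observable date is within 30 days of the second fill contribute no risk time: none with administrative censoring only, but 80,000 − 76,801 = 3,199 (4.0%) in the second scenario. They should be identified before matching, or their loss and the broken pairs reported by arm. Lastly, the cut corrects rates, but crude risk then refers to a window 30 days shorter and should be labelled so.

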Data during the baseline period will be used to confirm study eligibility and classification of exposure. The follow-up period will be used for identifying the outcome. This is illustrated in [Figure 1](#).

Figure 1

Study timeline

*Patients are allowed to enter the cohort between 28-September-2015 and 31-December-2018. The last allowable date for start of follow-up is 1-March-2019. The follow-up ends at the earliest occurrence of the outcome, or the first occurrence of inpatient death, disenrollment, or end of the study period (31-Mar-2019). A sensitivity analysis will employ an as-treated censoring approach to further censor upon discontinuation of index therapy or initiation of the other index treatment arm.

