9.7.1.2 Rates and Risks

● *Rate of Triple Therapy Initiation*

Among the unmatched and matched cohorts, rates of triple therapy use for each treatment group will be reported as the number of events (first per patient) divided by the total number of person-years at risk during follow-up. Comparative rates and corresponding 95% CIs will be reported as both the rate ratio and rate difference per 1,000 person-years at risk.

● *Risk of Triple Therapy Initiation*

Among the unmatched and matched cohorts, risk of triple therapy use for each treatment group will be reported as the number of events (first per patient) divided by the total number of patients at risk. Comparative risks and corresponding 95% CIs will be reported as both the risk ratio and risk difference per 1,000 person at risk.

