9.7.1.3 Comparative Effectiveness

● *Hazard Ratio for Triple Therapy Use Initiation*

Among both the basic propensity score matched and high dimensional propensity score matched cohort, Cox regression will be used to estimate the hazard ratios and 95% CI for Tiotropium/Olodenaterol compared to patients treated with Tiotropium during follow-up for time-to-first triple therapy initiation using an intention-to-treat censoring approach.

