9.7.3 Sensitivity Analyses

1. Less Stringent Qualifying Event Criterion

Instead of defining the event to qualify patients for inclusion based on two prescriptions within 60 days, patients may enter upon only one prescription. While some confidence is lost in whether the patients truly took their index medications, the less stringent qualifying event criterion will allow more patients to be included, increasing statistical power. Furthermore, the possibility of immortal time bias is also mitigated, since the time between prescriptions is no longer present.

2. As-treated Censoring

The analysis will use an as-treated approach for primary, secondary and further endpoint outcomes. In addition to the censoring criteria mentioned for the intention-to-treat approach (outcome, death, or end of data), patients will also be censored after medication discontinuation or switching over to the other arm.

3. Alternative algorithm for COPD

The analysis will use a different set of diagnosis codes for COPD (J43*, J44*) when selecting COPD patients. Compared to the primary analysis, this algorithm omits the diagnostic code for chronic bronchitis (J41*), as this code is commonly used by pulmonologists when prescribing Mucodyne to patients who do not actually have chronic bronchitis. While some true chronic bronchitis patients may be excluded, the selection of patient will increase specificity.

4. Asthma patients with doubt

Asthma patients with doubt are defined as patients with a diagnosis code for asthma and without evidence of any asthma specific treatment (ie., ICS, ICS/LABA). This sensitivity analysis will include patients identified with asthma with doubt.

5. ACOS sensitivity analysis

Patients that have evidence of asthma during the follow-up period will have their data censored on the date of asthma diagnosis during the follow-up period. This will ensure that they contribute information during their COPD disease trajectory up until the time they develop asthma. This approach will mitigate introducing immortal time bias for those patients with ACOS during the follow-up period.

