9.9 LIMITATIONS OF THE RESEARCH METHODS

This study will be conducted using hospital-based health insurance claims following the DPC payment system and is subject to certain limitations. One limitation is that these are based on a large, non-random convenience sample based in Japan, which may contain biases or lack generalizability to other populations. Data also come from a subset of hospitals in Japan, which would lead to failure to record events if patients visit medical centers not included in MDV's data sources (**Tanaka 2015**). Moreover, because healthcare is nationalized in Japan, the notion of enrolment is not applicable, and all patients are assumed to be observable throughout the global date range of the data. However, if a patient's emigration or mortality is not captured, then they would remain in the study despite not truly being eligible for any events, thereby leading underestimations of the risks and rates and possible bias in the hazard ratio if these patients are differentially distributed between the exposed and unexposed groups.

Another limitation of the study is that patients on monotherapy may escalate to double therapy before receiving the triple therapy. The patients starting on double therapy do not have this option. Therefore, patients on monotherapy may take longer to get to triple therapy than the patients on double therapy.

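### The primary analysis is given two incompatible ends of follow-up, last encounter and end of data; the second understates both arms' event rates, and material hazard-ratio bias needs leaving to differ by arm

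*Combined protocol and SAP*

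**What the plan says.** Section 9.2.1 defines the Follow-Up Period as "ending at the earliest occurrence of the outcome (use of triple therapy), or the first occurrence of inpatient death, disenrollment" or 31 March 2019. Enrolment does not exist as such in Japan, so the section substitutes a proxy: "end of enrolment = date of last inpatient/outpatient encounter will be used". The note to Figure 1 repeats the rule: "The follow-up ends at the earliest occurrence of the outcome, or the first occurrence of inpatient death, disenrollment, or end of the study period".

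The Censoring paragraph of section 9.3.2.1 gives a different list for the primary outcome: "Patients will be censored if they had an occurrence of any of the following: outcome (initiation of triple therapy), death, or end of data". Section 9.7.3, item 2, describes the intention-to-treat rule in the same way, as "the censoring criteria mentioned for the intention-to-treat approach (outcome, death, or end of data", and so does the abstract. Section 9.9 goes further: "all patients are assumed to be observable throughout the global date range of the data".

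The analysis sections do not choose. Section 9.7.1.2 defines the rate as events "divided by the total number of person-years at risk during follow-up". Section 9.7.1.3 fits the Cox model "during follow-up for time-to-first triple therapy initiation using an intention-to-treat censoring approach". The term follow-up points to section 9.2.1; the intention-to-treat term points to the list without disenrollment.

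**The concern.** The end of follow-up sets the denominator of the rates and the risk sets of the Cox model. Two programmers could each follow the protocol faithfully and produce different person-time.

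The choice matters because patients can drop out of sight. Section 9.4 says that data from different hospitals cannot be linked, and section 9.9 says that only in-hospital deaths are captured. Under the end-of-data rule, someone who changes hospital or dies at home is counted as event-free up to 31 March 2019. Section 9.9 concedes that such patients lower the rates and may bias the hazard ratio if they are unevenly spread between arms. It does not mention that section 9.2.1 already contains a rule limiting the problem.

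At stake are the absolute rates, the rate difference and, if leaving differs by arm, the hazard ratio. Section 9.3.2.1 even words the primary outcome as an incident rate.

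**Working it through.** **Inputs from the documents**
- One-year risks of 6% (Tio/Olo) and 10% (Tio), section 9.5.
- Entry from 28 September 2015 to 31 December 2018 and data end on 31 March 2019, section 9.2.1.
- Follow-up starts at the second prescription, section 9.2.1.

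**Assumptions**
- Constant event hazards and exponential leaving at rate λ, independent of event risk. The documents give no λ, so a range is shown.
- Second prescription at 30 days and uniform entry, so the time c from start of follow-up to data end is uniform from 0.164 to 3.42 years.

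**The plan's own figure.** Events = 4(1.960 + 1.282)²/(ln 1.73)² = 42.03/0.3004 = 140, against 141 stated in section 9.5. The hazards below come from the 6% and 10% directly. They imply 1/0.587 = 1.70, the abstract's value; the 1.7 versus 1.73 mismatch is a separate matter.

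**Hazards.** h = −ln(1 − p): 0.0619 for Tio/Olo and 0.1054 for Tio. That is 61.9 and 105.4 per 1,000 person-years, ratio 0.587, difference 43.5.

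**Rates under each rule.** With k = h + λ and a given c:
- recorded events per patient: (h/k)(1 − e^(−kc)), the same under both rules;
- person-time, censored at leaving: (1 − e^(−kc))/k, so the rate is exactly h;
- person-time, censored at end of data: h[(1 − e^(−kc))/k² − c·e^(−kc)/k] + c[1 − (h/k)(1 − e^(−kc))].

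Each is averaged over c. Example for λ = 0.2:
- Tio: 0.1371 events over 1.3011 years (105.4) or 1.6226 years (84.5).
- Tio/Olo: 0.0840 events over 1.3572 years (61.9) or 1.6893 years (49.7).

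**Cox hazard ratio.** Under the end-of-data rule the risk set is proportional to 1 − (h/k)(1 − e^(−kt)), while events accrue at h·e^(−kt), each multiplied by the probability that c exceeds t. Solving the large-sample score equation gives the last column.

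End-of-data censoring (rates per 1,000 person-years):

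| Leaving per year, Tio/Olo vs Tio | Tio/Olo rate | Tio rate | Rate ratio | Difference | Cox HR |
|---|---|---|---|---|---|
| none | 61.9 | 105.4 | 0.587 | 43.5 | 0.587 |
| 0.1 vs 0.1 | 55.3 | 94.0 | 0.588 | 38.7 | 0.590 |
| 0.2 vs 0.2 | 49.7 | 84.5 | 0.588 | 34.8 | 0.591 |
| 0.3 vs 0.3 | 45.0 | 76.4 | 0.589 | 31.4 | 0.592 |
| 0.2 vs 0.3 | 49.7 | 76.4 | 0.65 | 26.7 | 0.65 |
| 0.3 vs 0.2 | 45.0 | 84.5 | 0.53 | 39.5 | 0.54 |
| 0.2 vs 0.1 | 49.7 | 94.0 | 0.53 | 44.3 | 0.53 |
| 0.6 vs 0.3 | 34.5 | 76.4 | 0.45 | 41.9 | 0.46 |

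With equal leaving, rates fall by about 11%, 20% and 27%. Censoring at leaving returns 61.9, 105.4 and 0.587 in every row.

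**Simulation check** (2 million per arm, similar follow-up window, standard error of the log HR about 0.003). Equal leaving at 0.1: HR 0.589 at end of data, 0.587 at leaving. Tio/Olo 0.2 and Tio 0.3: 0.653 against 0.586. With no true effect, equal leaving gives 1.00, and Tio/Olo 0.2 with Tio 0.3 gives about 1.11.

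**Unequal follow-up length.** If Tio/Olo follow-up is capped at 2.0 years (assumed) and leaving is equal at 0.1, 0.2 or 0.3, the crude rate ratio under end-of-data censoring becomes 0.62, 0.64 or 0.67. The Cox HR stays near 0.59.

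**The case against.** The strongest reply is that section 9.2.1 is the formal definition and governs. It introduces the proxy precisely because enrolment does not apply, Figure 1 repeats it, and both analysis sections work within follow-up. On that reading the list in section 9.3.2.1 is shorthand, written to contrast intention-to-treat with as-treated censoring, and section 9.9 is a limitations paragraph rather than an instruction. This supports choosing the 9.2.1 rule. It does not remove the conflict: the shorter list appears in three places, section 9.9 adopts its logic, and no precedence is stated.

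A second reply is that the primary comparison is a hazard ratio, hardly affected when the arms leave equally, and that section 9.9 already discloses the risk. The first part stands and limits the claim. Disclosure, however, does not say which rule to program. The safeguards at entry (180 days of proxy enrolment, a second prescription, matching on hospital size, calendar year and service intensity) do not act on later leaving.

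Third, the last-encounter rule is not clean either. For patients still attending, the gap from last visit to 31 March 2019 is real at-risk time, which that rule drops. This stands.

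A reader might infer that the planned hazard ratio is biased. The documents give no leaving rate and no arm difference, so that is unsupported. Nor is the opposite exact: equal leaving does move a non-null hazard ratio, by about 1%.

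**Conclusion.** Wrong as written: one primary analysis, two ends of follow-up, and no statement of which governs. The conflict itself needs no assumption. Its numerical size does, because every leaving rate above is assumed and the true size is unknown.

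- **Rates.** The end-of-data rule lowers both, through patients who have left or died outside hospital. Recorded events, and so the crude risks of section 9.7.1.2, are the same under either rule.
- **Hazard ratio.** Equal leaving attenuates it only slightly at the planned risks. Material bias, in either direction, needs leaving to differ by arm.
- **Crude rate ratio.** It can also shift under equal leaving if follow-up length differs by arm. This matters mainly in the unmatched cohort, since calendar year enters the propensity score.
- **Rate difference.** It can shrink, stay the same or grow. A reader might look for a threshold such as Tio/Olo patients leaving twice as fast, but none holds generally: 0.2 vs 0.1 gives 44.3, above 43.5, while 0.6 vs 0.3 gives 41.9, below it.

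**What to change.** State one rule, that of section 9.2.1, in section 9.3.2.1, section 9.7.3 item 2, the abstract and section 9.9. Follow-up ends at the earliest of outcome, inpatient death, last inpatient or outpatient encounter, or 31 March 2019, and an event dated on the last encounter counts. Remove the full-observability assumption from the main analysis and run end-of-data censoring as a sensitivity analysis.

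Report by arm, among patients without outcome or inpatient death, the time from last encounter to 31 March 2019: median, IQR and share above 90 days. The cut-off matters. With assumed visits every 30 to 90 days, 97-99% of patients have a last encounter before that date even if nobody leaves. The share above 90 days is 0% with no leaving and 15-16%, 27-28% and 36-38% at 0.1, 0.2 and 0.3 per year.

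Cost: wording in four places, one extra run and one table row; no recorded event is lost. Downside: last-encounter censoring drops some at-risk time for patients still attending, gives no person-time to patients whose second prescription is their last encounter, and may be informative. With non-informative leaving and the same assumed visit spacing, its rates came within 2% of the planned values. The sensitivity run brackets the rest.
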